## **6.4. Analysis of safety**

### **6.4.1. Analysis of safety planned in the protocol**

#### **6.4.1.1. Within groups assessment**

The analysis will be based on the ES on each treatment groups separately.

The percentage of subjects with at least one local AE (solicited and unsolicited), with at least one general AE (solicited and unsolicited) and with any AE during the 7-day or 30-day follow-up period will be tabulated with exact 95% confidence interval (CI) after each vaccine dose and overall. The percentage of doses followed by at least one local AE (solicited and unsolicited), by at least one general AE (solicited and unsolicited) and by any AE during the 7-day or 30-day follow-up period will be tabulated, overall vaccination course, with exact 95% CI. The same computations will be done for Grade 3 AEs, for any AEs considered related to vaccination and for any Grade 3 AEs considered related to vaccination.

The percentage of subjects reporting each individual solicited local AE (any grade, Grade 2, Grade 3, resulting in a medically attended visit) and solicited general AE (any grade, Grade 2, Grade 3, any related, Grade 2 related, Grade 3 related, resulting in medically attended visit) during the 7-day follow-up period (Day 1-7) will be tabulated for each group after each vaccine dose and overall. Similarly, the percentage of doses followed by each individual solicited local and general AE and their sub-categories, will be tabulated, overall vaccination course, with exact 95% CI.

For fever, the number and percentage of subjects reporting fever by half degree (°C) cumulative increments during the 7-day follow-up period (Day 0-6) will be tabulated for each group after each vaccine dose and overall. Similar tabulations will be performed for any fever with a causal relationship to vaccination, Grade 3 (> 39.5°C) causally related fever and for any fever resulting in a medically attended visit. In addition, the prevalence of any and Grade 3 fever will be presented graphically over time after vaccination.

The percentage of subjects with unsolicited AEs within 30 days (Day 1-30) after each vaccine dose (overall doses) with its exact 95% CI will be tabulated by group and by MedDRA preferred term. Similar tabulation will be done for Grade 3 unsolicited AEs, for any causally related unsolicited AEs, for Grade 3 causally related unsolicited AEs and for unsolicited AEs resulting in a medically attended visit. The verbatim reports of unsolicited AEs will be reviewed by a physician and the signs and AEs will be coded according to the MedDRA Dictionary Version 20 for Adverse Reaction Terminology. Every verbatim term will be matched with the appropriate Preferred Term.

The percentage of subject with episode of spontaneous or excessive bleeding (AE of specific interest), during a 30-day follow-up period after each vaccination will be tabulated by group according to associated PT code presented in Section 12. The percentage of subjects with RSV-LRTI (AE of specific interest) from Dose 1 up to Day 365 and from Dose 1 up to study conclusion (Day 730) will be tabulated by group according to associated PT code presented in Section 12.

The percentage of subjects with SAE within 30 days (Day 1-30) after each vaccine dose with its exact 95% CI will be tabulated by group and by MedDRA preferred term. Similar table will be generated for SAE from Dose 1 up to Day 61, from Dose 1 up to Day 366 and from Dose 1 up to Day 731.

SAEs reported throughout the study and AE of specific interest will be described in detail.

The percentage of subjects using concomitant medication (any medication, any antipyretic/ analgesic and any antipyretic taken prophylactically, respectively) during the 7-day follow-up period (Day 1-7) and during the 30-day follow-up period (Day 1-30) will be summarized by group after each vaccine dose and overall.

For each group and for each hematology and biochemistry parameter:

- The percentage of subjects having hematology and biochemistry results below/above/within the local laboratory normal ranges will be tabulated by timepoint and toxicity grading scale.
- The maximum grading from Screening up to Visit 9 (Day 61) will be tabulated by grading the safety laboratory values according to toxicity criteria Grading scale adapted from [Division of AIDS, 2003], [Division of AIDS, 2004] and [Division of AIDS, 2007].
- For eosinophils, basophils, and monocytes, summary statistics (min, max, standard deviation, mean and median) will be presented as there is no grading provided for these parameters.

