1.3. Benefit : Risk Assessment

Approximately half of the infants (*between 32 and 48*) in this study will be exposed to the ChAd155-RSV vaccine, whereas the other infants will receive a placebo (**Amended 10 December 2017**).

Please refer to the current IB for the summary of potential risks and benefits of ChAd155-RSV vaccine.

The following section outlines the risk assessment and mitigation strategy for this study protocol:

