 - Epoch 002: follow-up starting at Visit 10 (Day 365) and ending at Visit 11 (Day 730).

Any safety, immunogenicity and disease surveillance data collected beyond Visit 9 (Day 60) will be collected in Epoch 002.

- Primary completion Date: Visit 9 (Day 60).
Refer to [glossary of terms](#) for the definition of primary completion date.
- End of Study: Last testing results released of samples collected at Visit 11 (Day 730).*

* Up to Visit 11 (Day 730), there will be monthly nasal swab to detect asymptomatic RSV infections during the RSV season and if following active or a passive surveillance contacts, a subject presents symptoms of RTI, a nasal swab will be collected.

Refer to [glossary of terms](#) for the definition of end of study.

- Study groups: throughout the three steps, infants will be randomized in two groups to receive either ChAd155-RSV vaccine or placebo ([Table 1](#)).

Table 1 Study groups and epochs foreseen in the study (Amended 10 December 2017)

Step	Study groups	Number of subjects*	Age (Min/Max)	Epochs	
				Epoch 001	Epoch 002
1	RSV-Ld	~ 16	12 months - 23 months	x	x
	Placebo-Ld	~ 16	12 months - 23 months	x	x
2	RSV-Md	~ 16	12 months - 23 months	x	x
	Placebo-Md	~ 16	12 months - 23 months	x	x
3	RSV-Hd	~ 16	12 months - 23 months	x	x
	Placebo-Hd	~ 16	12 months - 23 months	x	x

RSV-Ld: low dose ChAd155-RSV vaccine (5×10^9 vp); **RSV-Md:** middle dose ChAd155-RSV vaccine (1.5×10^{10} vp); **RSV-Hd:** high dose ChAd155-RSV vaccine (5×10^{10} vp).

***The target will be to enroll up to 96 RSV-seropositive infants aged 12 to 23 months at the time of first vaccination (unless the dose escalation IDMC decision can be made based on the evaluation of accumulating safety data on fewer subjects) to ensure that at least 64 infants receive two doses of study vaccine (ChAd155-RSV or Placebo) (see Section 5.1). Then the number of subjects at each step will be at least 16 (approximately 8 subjects per group) at steps 1 and 2 and 32 (approximately 16 subjects per group at step 3) (Amended 10 December 2017).**

Table 2 Study groups and treatment foreseen in the study

Treatment name	Volume administered	Vaccine/Product name	Study Groups					
			Step 1		Step 2		Step 3	
			RSV-Ld	Placebo-Ld	RSV-Md	Placebo-Md	RSV-Hd	Placebo-Hd
ChAd155 5x10 ⁹ vp	0.5 ml	ChAd155-RSV	X					
ChAd155 1.5x10 ¹⁰ vp	0.15 ml	ChAd155-RSV			X			
ChAd155 5x10 ¹⁰ vp	0.5 ml	ChAd155-RSV					X	
Placebo 0.5	0.5 ml	Formulation buffer S9b		X				X

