11.4. Determination of sample size

No hypothesis driven sample size calculation was conducted due to the nature of descriptive summary of the study objectives. The sample size of 32 subjects per dose cohort/Step, randomized 1:1 to vaccine or placebo, was based on conventional study designs for Phase 1/2 trials. Specifically, if no adverse event was observed among 16 RSV vaccinated subjects, the exact, two-sided 95% confidence interval (CI) would rule out an AE rate of 20% or more; if the incidence rate of AEs is more than 10%, there will still be more than an 80% chance of observing at least one subject with this AE. Combining all RSV vaccinees across all dose levels, there will be more than a 99% chance of observing at least one subject with this AE.

Furthermore, with 16 RSV vaccinees, the maximum width of a 95% CI for the proportion of subjects with adverse events among 16 vaccinees is about 50% (see [Figure 5](#)). (Amended 10 December 2017)

[Figure 5](#) illustrates the precision on the percentage of subjects with symptoms following vaccination.

Figure 5 Exact 95% confidence interval on the percentage of subjects with adverse events following vaccination for 16 subjects per group

Taking the a priori safety concern of thrombocytopenia, both Frequentist and Bayesian approaches will be applied here to provide complementary assurance on the possibility to exclude a signal based on the accumulated safety data. The Frequentist approach examines the statistical power to rule out a significant decrease in platelet counts due to vaccination that would suggest a four-fold or greater increase in the risk of a Grade 3 or higher thrombocytopenia with 16 subjects per dose cohort. The Bayesian approach calculates the posterior predictive probability of not observing any subject with a Grade 3 or higher thrombocytopenia among the future 16 subjects by basing it on what we have observed in the first 16 subjects.

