#### **6.4.1.2. Between groups assessment**

Exploratory comparisons between the investigational RSV groups and the Placebo groups will be done in terms of the percentage of subjects, overall doses, reporting any Grade 2/3 AE during the 7-day follow-up period (Day 1-7) after vaccination, and/ or any fever  $>38.5^{\circ}\text{C}$  during the 7-day follow-up period (Day 1-7) after vaccination, and/ or any vaccine-related SAE during the 7-day follow-up period (Day 1-7) after vaccination.

The standardized asymptotic 95% CI for the following differences will be computed:

- RSV\_Ld minus Placebo\_Ld
- RSV\_Md minus Placebo\_Md
- RSV\_Hd minus Placebo\_Hd

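### Primary safety is reported in six separate groups with three within-step differences only; a supplementary pooled vaccine-versus-placebo summary, stratified by step, should be added

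*SAP*

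**What the plan says.** - SAP 6.4.1.1, on AEs, SAEs, events of specific interest and laboratory results: "The analysis will be based on the ES on each treatment groups separately".
- SAP 6.4.1.2: "The standardized asymptotic 95% CI for the following differences will be computed", followed by low, middle and high dose, each minus its own placebo group. Template 27 has the same three rows. It covers one composite over the 7 days after vaccination: Grade 2/3 AE, fever above 38.5°C or vaccine-related SAE.
- The footnotes to the AE, SAE, bleeding and laboratory templates list six groups. Where a Total column appears, it mixes vaccine and placebo.
- Protocol 11.8.2 describes the comparison as RSV groups minus Placebo groups, which can be read as pooled or by step. The SAP settles it by step, and SAP 9 does not mention the choice.
- Pooling is planned elsewhere. SAP 6.2.1.1 (CMI) and SAP 6.3 (RSV incidence and severity) use pooled RSV and pooled Placebo, and SAP 10 defines the labels.
- Protocol 11.4: "The sample size of 32 subjects per dose cohort/Step, randomized 1:1 to vaccine or placebo, was based on conventional study designs for Phase 1/2 trials". It justifies that size with 16 vaccinees per group ("if the incidence rate of AEs is more than 10%, there will still be more than an 80% chance" of seeing at least one case) and then adds: "Combining all RSV vaccinees across all dose levels, there will be more than a 99% chance".
- Protocol section 3, footnote to Table 1, gives the step sizes after Amendment 4 as "at least 16 (approximately 8 subjects per group) at steps 1 and 2", with about 16 per group in Step 3. Protocol 1.3 puts total vaccinees between 32 and 48.

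**The concern.** Safety up to 30 days after Dose 2 is the primary objective. Every vaccinee has concurrent placebo controls randomised 1:1 within the same step, so a vaccine-versus-placebo contrast over all steps is available without new data. The plan produces this contrast for no safety outcome outside RSV illness, and even there it shows pooled proportions without a difference.

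This matters for effects that may be shared across doses. Protocol 1.3.1 raises one: platelet falls seen with this vector before clinical use and with a similar adenoviral vector in adults. An effect of that kind would be read from three wide intervals, two of which may come from about 8 infants per arm. If pooling is not prespecified, the decision to pool could be taken after the statistician is unblinded at the Day 61 analysis (SAP 8.1).

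**Working it through.** **Inputs.**
- Full step: 16 vaccinees and 16 placebo (Protocol 11.4).
- Minimum: about 8 per group in Steps 1 and 2, and 16 in Step 3 (Protocol section 3).
- Total vaccinees: 8 + 8 + 16 = 32 at the minimum and 3 × 16 = 48 at the maximum, as in Protocol 1.3.
- Event rate for detection: 10% (Protocol 11.4).
- Interval for a difference: two-sided 95% standardised asymptotic (SAP 11.2). It is computed here as the Miettinen-Nurminen score interval, which is my reading of the method named there.
- AE rates for the differences: none in the documents. The values 12.5%, 25% and 50% are assumptions.

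**1. The plan's own detection figures.** P(at least one case) = 1 − 0.9^n.
- n = 16: 1 − 0.1853 = 81.5%. The stated figure above 80% reproduces.
- n = 48: 1 − 0.0064 = 99.4%. The stated figure above 99% reproduces.
- n = 32: 1 − 0.0343 = 96.6%. The stated figure does not hold at the Amendment 4 minimum. It needs 44 vaccinees (99.03%; 43 gives 98.92%).
- n = 8: 1 − 0.4305 = 57.0%, against the 80% stated for a group of 16.

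**2. Upper exact limit when no event is seen.** Limit = 1 − 0.025^(1/n): 36.9% (n = 8), 20.6% (16), 10.9% (32), 7.4% (48).

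**3. 95% interval for vaccine minus placebo, in percentage points.** The pooled columns treat the total as one table. With balanced arms and similar rates across steps, a stratified interval would be close to this.

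| Assumed rates | 8 v 8 | 16 v 16 | 32 v 32 (pooled, minimum) | 48 v 48 (pooled, full) |
|---|---|---|---|---|
| 12.5% v 12.5% | ±39.2 | ±26.5 | ±17.8 | ±14.2 |
| 25% v 25% | ±42.6 | ±30.4 | ±21.5 | ±17.5 |
| 50% v 50% | ±45.2 | ±33.2 | ±24.0 | ±19.7 |
| 50% v 25% | −23.2 to 63.5 | −9.1 to 54.0 | 1.1 to 46.3 | 5.6 to 42.7 |

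At 25%, pooling at the minimum halves the half-width of an 8 v 8 step (42.6 / 21.5 = 1.98). At full size it divides that of a 16 v 16 step by 30.4 / 17.5 = 1.74, close to √3. At 50% v 25% the interval includes zero at 8 or 16 per arm and excludes it at 32 or 48. The Newcombe hybrid score interval gives the same pattern: −7.9 to 51.5 at 16 per arm and 5.6 to 41.9 at 48.

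**4. What pooling does to an effect confined to the high dose.** The high dose makes up 16/48 = one third of vaccinees at full size and 16/32 = one half at the minimum. A 25-point excess at the high dose only would appear as 25/3 = 8.3 or 25/2 = 12.5 points in the pooled difference. This is why pooling can only supplement the by-dose results.

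**The case against.** The by-dose layout fits the primary objective, which concerns three dose levels over a tenfold range. A pooled estimate is a mixture, and its dose weights depend on when the IDMC lets Steps 1 and 2 stop. Pooled local-reaction columns would combine 0.15 mL and 0.5 mL injections. All comparisons are declared descriptive, unadjusted and to be read with caution (Protocol 11.11, SAP 7). The IDMC sees unblinded data and reviews the whole safety set of Steps 1 to 3 together. A reader can add the columns, and ±17.5 to ±21.5 points is still imprecise. All of this stands, and it limits the point to a supplementary display. Adding columns by hand, however, gives neither a prespecified interval nor stratification by step.

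Two stronger readings are tempting:

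- **That the sample size relies on pooling, so that the SAP contradicts the protocol.** Protocol 11.4 disclaims a hypothesis-driven calculation and rests on convention and 16 vaccinees per group. The combined figure is an added probability in vaccinees alone. It does not depend on table layout and promises no randomised contrast.
- **That safety is nowhere pooled.** RSV-LRTI is an event of specific interest, and Protocol section 4 treats the case-definition analysis as complementary safety analysis. SAP 6.3 already shows it by pooled arm.

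**Conclusion.** The point holds as a low-cost improvement to the primary safety analysis. For solicited and unsolicited AEs, SAEs, bleeding events and laboratory grades, the SAP text and templates plan no pooled-arm summary and no pooled difference. The full table-of-contents file for the outputs is not among the documents, so this rests on the SAP text and its mock tables.

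At an assumed 25% rate the cost is an interval of ±42.6 or ±30.4 points per step, where ±21.5 or ±17.5 is available. The halving is insensitive to the assumed rate over 12.5% to 50%. Whether a real effect would be missed in the step tables and seen when pooled depends on rates that the documents do not give. The 50% v 25% case is an illustration only.

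Separately, the figure above 99% in Protocol 11.4 is true for 44 to 48 vaccinees and not for 32 to 43. The documents do not support calling the by-dose analysis wrong; it answers the dose-specific question and should remain the main display.

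**What to change.** 1. Keep the by-dose results as the main display.
2. Add pooled RSV and pooled Placebo columns to the main AE, SAE, bleeding-event and laboratory-grade tables, using the labels in SAP 10.
3. Add to Template 27 a pooled RSV minus pooled Placebo difference with a 95% CI stratified by step. Template 27 covers only the 7-day composite, so give the same stratified difference for SAEs and for Grade 3 or higher laboratory abnormalities.
4. Name the stratified interval method in SAP 11.2, which now cites a method for two independent proportions only.
5. Footnote the pooled results: they are supplementary, they can dilute an effect confined to the high dose, their dose mix depends on when Steps 1 and 2 stop, and local-reaction columns mix 0.15 mL and 0.5 mL injections.
6. Record the choice in SAP 9 before the Day 61 unblinding.
7. Restate the combined detection probability in Protocol 11.4 as 96.6% to 99.4% for 32 to 48 vaccinees.

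The cost is SAP wording, extra columns and a few added rows. No new data and no design change are needed.

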Placebo 0.15	0.15 ml	Formulation buffer S9b				X		

RSV-Ld: low dose ChAd155-RSV vaccine (5 x 10⁹ vp); **RSV-Md:** middle dose ChAd155-RSV vaccine (1.5 x 10¹⁰ vp); **RSV-Hd:** high dose ChAd155-RSV vaccine (5 x 10¹⁰ vp).

- Control: placebo control (Formulation buffer S9b).
- Vaccination schedule(s): two IM vaccine doses administered according to a 0, 1-month schedule (i.e. at Day 0 and Day 30).
- Treatment allocation: infants will be randomized using a randomization system on internet (SBIR) at first vaccination.
- Blinding: observer-blind in Epoch 001 and single-blind in Epoch 002.

Table 3 Blinding of study epochs

Study Epochs	Blinding
Epoch 001	observer-blind
Epoch 002	single-blind

- Sampling schedule:
 - Blood samples for **biochemistry** will be taken from all infants at Screening (up to 29 days before first vaccination to Day 0) and on Day 30, and Day 60 (refer to [Table 11](#) for the list of parameters to be tested). Blood samples for **hematology** will be taken from all infants at Screening (up to 29 days before first vaccination to Day 0) and on Day 1, Day 30, Day 31, and Day 60 (refer to [Table 11](#) for the list of parameters to be tested). Day 7 hematology testing will be performed if any \geq Grade 1 for platelet decrease is detected on Day 1 after vaccination, to ensure its resolution. Similarly, hematology testing on Day 37 will be performed if any \geq Grade 1 for platelet decrease is detected on Day 31. A clinical examination with special attention given to detection of spontaneous bleeding or easy bruising and evidence of bruising or petechiae will be performed by the investigator/study staff on Day 1, Day 3 and Day 7 after each vaccination (i.e. Day 1, Day 3, Day 7, Day 31, Day 33, and Day 37). The visits on Day 3 and Day 33 may be replaced by a phone call by the investigator/study staff to inquire of the infants' general health and to solicit reports of a rash, spontaneous bleeding or easy bruising. On Day 1, and Day 31, special attention will also be given to the detection of petechiae or evidence of petechiae induced by the tourniquet. This special attention to detection of petechiae or evidence of petechiae induced by the tourniquet will also be given on Day 7 and/or Day 37 in case hematology

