Figure 2 Schematic overview of required additional hematology and biochemistry testing during the study

Note: For safety reasons and specifically for further investigation of an AE of specific interest (suspected bleeding or low platelet count), blood can be re-sampled for hematology and biochemistry assessment.

6.6.11.3. Nasal swab and other specimen for local assay**Nasal swab and other specimen for local assay collected during assessment visit**

If during passive or active surveillance contact, the investigator/study staff assesses that an infant presents a potential RSV-RTI (refer to 9.2), a nasal swab and another specimen for local assay will be collected during an assessment visit:

- The nasal swab will allow assessing the potential RSV infection by quantitative RT-PCR at sponsor laboratory.
- The specimen for local assay will allow assessing the potential RSV infection and RVP at a local routine laboratory, where available. The specimen type will depend on the assay run locally.

Nasal swab collected to detect asymptomatic RSV infections

During RSV season, there will be monthly nasal swabs to detect asymptomatic RSV infections. These nasal swabs will allow assessing the potential RSV infection by quantitative RT-PCR at sponsor laboratory.

Refer to the SPM for more details about nasal swab.

6.6.12. Detection of spontaneous bleeding or easy bruising and evidence of bruising or petechiae

Subjects' parent(s)/LAR(s) will be instructed to contact the investigator/study staff if their child presents symptoms of spontaneous bleeding or easy bruising or if their child develops a rash in the month following vaccination, in order to detect any thrombocytopenic petechiae or purpura. Refer to Sections 9.1.5 and 9.4.3 for reporting of adverse events of specific interest (spontaneous or excessive bleeding).

At Visit 2 (Day 1), Visit 3 (Day 3)*, Visit 4 (Day 7), Visit 6 (Day 31), Visit 7 (Day 33)*, and Visit 8 (Day 37), the investigator will perform a clinical examination with special attention given to detection of spontaneous bleeding or easy bruising and evidence of bruising or petechiae. Episodes of spontaneous bleeding or easy bruising and evidence of bruising or petechiae will be recorded in the eCRF.

* The visits on Day 3 and Day 33 may be replaced by a phone call by the investigator/study staff to inquire of the infants' general health and to solicit reports of a rash, spontaneous bleeding or easy bruising.

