6.6.13. Detection of petechiae or evidence of petechiae induced by the tourniquet

At Visit 2 (Day 1), Visit 6 (Day 31), the investigator will perform an examination of the limb where the tourniquet for blood sample has been placed in order to detect petechiae or evidence of petechiae induced by the tourniquet. This special attention to detection of petechiae or evidence of petechiae induced by the tourniquet will also be given at Visit 4 (Day 7) and/or Visit 8 (Day 37) in case hematology testing will be performed on that day. Episodes of petechiae will be recorded in the eCRF.

These episodes might be reported as AE based on the investigators clinical judgment.

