9.1. Safety definitions

9.1.1. Definition of an adverse event

An AE is any untoward medical occurrence in a clinical investigation subject, temporally associated with the use of a medicinal product, whether or not considered related to the medicinal product.

An AE can therefore be any unfavorable and unintended sign (including an abnormal laboratory finding), symptom, or disease (new or exacerbated) temporally associated with the use of a medicinal product. For marketed medicinal products, this also includes failure to produce expected benefits (i.e. lack of efficacy), abuse or misuse.

Examples of an AE include:

- Significant or unexpected worsening or exacerbation of the condition/indication under study.

- Exacerbation of a chronic or intermittent pre-existing condition including either an increase in frequency and/or intensity of the condition.
- New conditions detected or diagnosed after investigational vaccine(s) administration even though they may have been present prior to the start of the study.
- Signs, symptoms, or the clinical sequelae of a suspected interaction.
- Signs, symptoms, or the clinical sequelae of a suspected overdose of either investigational vaccine(s) or a concurrent medication (overdose per se should not be reported as an AE/SAE).
- Signs, symptoms temporally associated with vaccine(s) administration.
- Significant failure of expected pharmacological or biological action.

AEs to be recorded as endpoints (solicited AEs) are described in Section 9.1.3. All other AEs will be recorded as UNSOLICITED AEs.

Examples of an AE DO NOT include:

- Medical or surgical procedures (e.g. endoscopy, appendectomy); the condition that leads to the procedure is an AE/SAE.
- Situations where an untoward medical occurrence did not occur (e.g. social and/or convenience admission to a hospital, admission for routine examination).
- Anticipated day-to-day fluctuations of pre-existing disease(s) or condition(s) present or detected at the start of the study that do not worsen.
- Pre-existing conditions or signs and/or symptoms present in a subject prior to the first study vaccination. These events will be recorded in the medical history section of the eCRF.

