9.1.3.2. Solicited general adverse events

The following general AEs will be solicited:

Table 17 Solicited general adverse events

Infant
Drowsiness
Fever*
Irritability/Fussiness
Loss of appetite

* Fever is defined as temperature $\geq 37.5^{\circ}\text{C}/99.5^{\circ}\text{F}$ for oral, axillary or tympanic route, or $\geq 38.0^{\circ}\text{C}/100.4^{\circ}\text{F}$ for rectal route. The preferred route for recording temperature in this study will be axillary.

Note: Temperature will be recorded in the evening. Should additional temperature measurements be performed at other times of day, the highest temperature will be recorded in the eCRF.

9.1.4. Clinical laboratory parameters and other abnormal assessments qualifying as adverse events or serious adverse events

In absence of diagnosis, abnormal laboratory findings (e.g. clinical chemistry, hematology, urinalysis) or other abnormal assessments (e.g. physical examination) that are judged by the investigator to be clinically significant will be recorded as AE or SAE if they meet the definition of an AE or SAE (refer to Sections 9.1.1 and 9.1.2). Clinically significant abnormal laboratory findings or other abnormal assessments that are present at baseline and significantly worsen following the start of the study will also be reported as AEs or SAEs.

The investigator will exercise his or her medical and scientific judgment in deciding whether an abnormal laboratory finding or other abnormal assessment is clinically significant.

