9.2.5. Subject hospitalized for LRTI

Subjects admitted to hospital and treated for an LRTI will be documented fully as SAEs. In addition to establish the severity of the illness, the eCRF screen corresponding to the assessment visit will be completed as fully as possible from medical records. Signs and symptoms to be recorded in the eCRF are listed in the SPM. Study staff will collect a nasal swab for all the subjects who have been hospitalized with a RTI for analysis at sponsor laboratory. All subjects with clinical suspicion of LRTI must be tested for RSV and RVP using locally available test. Note: all subjects experiencing an RSV-LRTI must be reported as an AE of specific interest in an expedited manner (refer to Section 9.4).

Study staff will also collect a blood sample to be stored at sponsor's laboratory for future assessment of mechanism of illness (potential ERD). This will be done only for RSV-positive subjects using a locally available RSV test.

9.3. Detecting and recording adverse events, adverse events of specific interest and serious adverse events

9.3.1. Time period for detecting and recording adverse events, adverse events of specific interest and serious adverse events

All AEs starting within 30 days following administration of each dose of study vaccine (Day 0 to Day 29) must be recorded into the appropriate section of the eCRF, irrespective of intensity or whether or not they are considered vaccination-related.

The time period for collecting and recording SAEs will begin at the first receipt of study vaccine and will end at study conclusion. See Section 9.4 for instructions on reporting of SAEs.

All AEs/SAEs leading to withdrawal from the study will be collected and recorded from the time of the first receipt of study vaccines.

In addition to the above-mentioned reporting requirements and in order to fulfill international reporting obligations, SAEs that are related to study participation (i.e. protocol-mandated procedures, invasive tests, a change from existing therapy) or are related to a concurrent GSK medication/vaccine will be collected and recorded from the time the subject consents to participate in the study until she/he is discharged from the study.

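### Bruising and petechiae found at scheduled examinations but not reported as AEs have no by-group summary in the visible SAP at Day 61 (low severity)

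*SAP*

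**What the plan says.** Protocol 6.6.12 requires an examination for bleeding, bruising and petechiae on Days 1, 3, 7, 31, 33 and 37; Days 3 and 33 may be a phone call. It then says: "Episodes of spontaneous bleeding or easy bruising and evidence of bruising or petechiae will be recorded in the eCRF". Protocol 6.6.13 adds an examination of the tourniquet limb on Days 1 and 31, and on Days 7 and 37 if hematology is drawn. These petechiae are also recorded, and of them it says: "These episodes might be reported as AE based on the investigators clinical judgment".

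Recording a finding is therefore a separate step from reporting an AE. Protocol 9.1.4 leaves it to the investigator's medical and scientific judgment "in deciding whether an abnormal laboratory finding or other abnormal assessment is clinically significant". The AE net is nonetheless wide. Under Protocol 9.1.1, "An AE can therefore be any unfavorable and unintended sign", and under 9.3.1 AEs within 30 days of each dose "must be recorded into the appropriate section of the eCRF, irrespective of intensity".

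On the analysis side, SAP 6.4.1.1 opens: "The analysis will be based on the ES on each treatment groups separately". Its bleeding item is "The percentage of subject with episode of spontaneous or excessive bleeding (AE of specific interest), during a 30-day follow-up period after each vaccination", identified through the preferred terms in SAP Section 12. The Day 61 row of SAP Table 3 names solicited and unsolicited AEs, hematology and biochemistry, the bleeding AE of specific interest, and SAEs. The examination data are named in SAP 13.1 only, as individual listing Appendix Table IIE. SAP 8.1 states that the Day 61 and Day 366 analyses provide no individual listings. (SAP Day 61 is protocol Day 60, because the SAP adds one to each day.)

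**The concern.** Thrombocytopenia is the safety concern named in advance in Protocol 11.4. Protocol 1.2.4.3 gives earlier hematology observations, including a transient platelet drop in rabbits with this vaccine, as the reason for these examinations. The trial therefore collects a clinical sign for a named risk, in both arms and on a fixed schedule.

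Such a sign is hard to read without the control arm. Toddlers bruise, so single cases mean little, while a count in vaccinees against placebo can be interpreted. If only AE-reported findings are counted, the comparison also depends on each investigator's threshold for calling a bruise or petechia an AE. At stake is a descriptive placebo comparison at the first analysis, from data already in the database.

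**Working it through.** No arithmetic applies, because the point concerns an absent summary. The check follows each kind of finding from the protocol procedure to its output in the SAP.

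| Finding | Output in the SAP | By group at Day 61? |
|---|---|---|
| Bruising or petechiae reported as an unsolicited AE | Unsolicited AE table (Template 22) | Yes |
| Reported events with a bleeding term in SAP Section 12 (petechiae and haematoma terms included) | Bleeding table (Template 28); AE listing (Template 35) | Yes, in the table |
| Platelet counts, scheduled and unscheduled | Templates 24 and 25 | Yes |
| Bruising or petechiae on examination, not reported as an AE | Appendix Table IIE listing | No |
| Tourniquet petechiae, not reported as an AE | Appendix Table IIE listing | No |

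1. **The last two rows can occur.** Protocol 6.6.12 and 6.6.13 record findings in the eCRF. Protocol 6.6.13 (tourniquet petechiae) and 9.1.4 (other abnormal assessments) leave AE status to judgment.
2. **The bleeding table cannot pick them up.** It works through coded preferred terms, which exist only for reported events. Template 35 is likewise limited to AEs.
3. **No other table does.** Nothing in SAP 6.4, the Day 61 row of Table 3 or Templates 1 to 56 summarises the examinations by group.
4. **The listing does not fill the gap at Day 61.** SAP 8.1 withholds individual listings then. Notes allowing a group-blinded listing at Day 61 stand under Templates 31 (unscheduled safety visits) and 32 (SAEs), not under Appendix Table IIE.
5. **The platelet safeguard stays in place.** Hematology is drawn from all infants at screening "and on Day 1, Day 30, Day 31, and Day 60" (Protocol Section 3). Days 7 and 37 are added after a platelet decrease of Grade 1 or worse on Day 1 or 31. Clinical suspicion of low platelets can lead to an unscheduled visit (Protocol Table 5), for which Template 24 has rows. Each limb examination falls on a day with a hematology draw.

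On size, the documents give no frequency for findings recorded but not reported as AEs. Multiplying an assumed rate by 64 to 96 infants would only restate the assumption. Detection probabilities for arms of 8 or 16 describe group size and are the same with or without the table. Group size does support a pooled display: vaccinees number at least 8 + 8 + 16 = 32 and at most 16 + 16 + 16 = 48 across the three steps.

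**The case against.** The strongest reply is that nothing planned has been dropped. The listed endpoint is the bleeding AE of specific interest, and Protocol 11.8.1 plans no summary of examination findings. This stands: the point is an improvement, not a deviation.

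Second, little may be left over. With a broad AE definition and recording irrespective of intensity, the unreported findings are mainly those judged not clinically significant, plus tourniquet petechiae. This also stands, and it limits the importance of the point.

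Third, the underlying risk is measured directly by platelet counts tabulated by group, and safety decisions during dosing rest with committees that see unblinded data. A reader might infer from the gap that a thrombocytopenia signal could go unseen or that dose escalation is less safe. The documents do not support that.

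Fourth, the full table list is in a separate TFL TOC that is not among the documents, so absence is not proven. This stands only in part. SAP Section 10 says study-specific mocks are in the SAP's own annex, and none of those covers these examinations.

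Fifth, the final report will contain all data, so a by-arm count could be made from the listing then. Since Templates 31 and 32 are produced group-blinded at Day 61, a blinded Appendix Table IIE at that point is not clearly excluded either. This is fair, but a blinded listing gives no comparison with placebo, and a later hand count is not a prespecified summary.

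Last, small arms carry an unblinding risk, because investigators see these signs themselves. This stands and shapes the fix.

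**Conclusion.** The point holds as a low-severity, cheap improvement. On the visible SAP, bruising, petechiae and tourniquet petechiae that are recorded but not reported as AEs get no by-group summary, and at Day 61 no listing is provided for them.

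Two stronger readings should be resisted. The plan does not ignore bleeding: events reported as AEs are tabulated by group. Nor are the examination data lost, since they remain in the database and in a named listing. No magnitude can be attached, because no event rate is given.

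The conclusion rests on two conditions: that some recorded findings are not reported as AEs, which the protocol allows but does not quantify, and that the unseen TFL TOC holds no such table.

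**What to change.** Add to SAP 6.4.1.1 and to the Day 61 row of Table 3 one descriptive table on the Exposed Set:

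- **Content:** number and percentage of infants, with exact 95% CI, with any bruising or petechiae on scheduled examination after each dose, regardless of AE status.
- **Tourniquet petechiae:** a separate line.
- **Denominator:** infants examined.
- **Columns:** each group, plus pooled RSV and pooled Placebo. The pooled labels already exist in SAP Section 10, but 6.4.1.1 analyses groups separately, so the pooling must be stated.
- **Leave out at Day 61:** by-visit detail for the small arms. A split between in-person examinations and Day 3/33 phone reports should be optional, because it depends on eCRF fields the documents do not show.

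If the TFL TOC already holds such a table, naming it in 6.4.1.1 and Table 3 is enough.

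The cost is one table from data already collected for Appendix Table IIE, plus SAP wording. No visit, sample or endpoint is added. There are two downsides: incidental toddler bruising will appear in both arms, and there is a small added risk of unblinding in arms of 8 to 16.
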